## 7. NOTATION OF TREATMENT GROUPS AND VISITS

### Notation of treatment groups

The following notation of **treatment groups** will be used throughout the report:

Full notation (as used in the study protocol)	Notation as used throughout all tables, listings, and figures
Dasiglucagon, liquid formulation, 1 mg/mL, 0.6 mL 1 mg lyophilized powder for reconstitution (GlucaGen®, Novo Nordisk)	dasiglucagon GlucaGen
Placebo treatment: Placebo, liquid formulation, 0.6 mL	Placebo

### Visit terminology

Visit	Notation as used throughout all tables, listings, and figures
V1 Screening	Screening
V2 Dosing	Dosing
V3 Follow up	Follow up

## 8. ANALYSIS SETS

For the statistical analysis, the randomized patients will be divided up into the following datasets. The following definitions are applicable:

### **Safety analysis set**

All patients who were randomized and received at least 1 dose of trial product. Treatment assignment will be based on the treatment actually received.

### **Full analysis set (FAS)**

All patients of the safety analysis set. Treatment assignment will be based on the randomized treatment. Assignment to the stratification factor injection site will be based on the planned

and not the actual used injection site.

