7.4.10 Blinding and breaking the blind

This is a double-blind trial. Dasiglucagon is available as a liquid formulation and GlucaGen® is available as a powder for reconstitution; they are therefore not identical in appearance. Unblinded trial personnel will be responsible for handling, preparing (according to the prescription from the IWRS), and administering the trial product, and the syringes used for administration will be wrapped in aluminum foil to maintain the blinding at bedside. Parents being in the room with their child must be instructed not to look while the unblinded staff is administering the injection. To maintain double-blind conditions, blinded trial personnel not involved in the administration of trial

products will perform all trial assessments at the trial center and is responsible for keeping the records strictly confidential and accessible only to the unblinded staff. However, unblinded personnel at the specialty laboratories will perform the exposure assessments and ADA assessments to make sure that dasiglucagon or GlucaGen® administration is matched with the applicable bioanalytical assay.

Treatment assignment will be kept strictly confidential and accessible only to authorized persons until after the time of unblinding (database lock). Codes with treatment assignment will however be readily available in the IWRS to the blinded personnel in case of an emergency.

The code for a particular patient may be broken in a medical emergency if knowing the identity of the treatment allocation would influence the treatment of the patient. The emergency code break can be performed using the IWRS. Whenever a code is broken, the person breaking the code must record the time, date and reason as well as his/her initials in the source documents.

The breaking of blinded codes in case of medical emergency for a patient should not unblind the trial personnel to the treatment information of other patients. The person performing the unblinding should inform as few people as possible about the result of the unblinding. All persons unblinded for a specific patient should be documented.

If the trial center needs to break the code, the medical monitor should, if at all possible, be contacted prior to breaking the code and the monitor must be notified within 24 hours after the code has been broken.

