12.2 Protocol deviations

Before data are released for statistical analysis, a treatment-masked review of all data will take place to identify protocol deviations that may potentially affect the results. This review will be performed without revealing to which trial product the patients were assigned. The masking of the trial products will be maintained for everyone involved in allocating patients to the analysis sets until data are released for statistical analysis. Furthermore, spurious outliers will be evaluated. In addition, protocol deviations that may potentially affect the results will be identified and it will be evaluated if patients and/or data should be excluded from the analysis. Protocol deviations will be classified as minor or major in a consistent way. Major deviations from the protocol may lead to the exclusion of a patient from the PPS.

Major protocol deviations may include deviations related to trial inclusion or exclusion criteria, conduct of the trial, patient management or patient assessment. Unless explicitly decided otherwise during the treatment-masked data review, the following will be considered major protocol deviations:

- Violation of one or more major inclusion/exclusion criteria
- Interruption of administration of trial product
- Significant deviation from time windows
- Incorrect treatment allocation
- Missing primary endpoint.

The violation of several major inclusion/exclusion criteria or the complete absence of efficacy data might lead to exclusion of the patient from the FAS. In that case, the decision should be taken at the treatment-masked data review meeting, and the exclusion from efficacy analysis will be justified in the signed notes of the meeting.

Obviously erroneous data points may be excluded from the analyses or re-analyzed (in case of, for example, serum concentrations). The decision to re-analyze or exclude data points from the statistical analysis is the joint responsibility of the sponsor and the trial statistician.

The patients or observations to be excluded and the reason for their exclusion will be documented and signed by those responsible prior to database release. The documentation will be stored together with the remaining trial documentation. The patients and observations excluded from analysis sets, and the corresponding reasons, will be described in the clinical trial report.

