Visit	Time Point	Class	dasiglucagon (N=xxx)	GlucaGen (N=xxx)	Placebo (N=xxx)	Total (N=xxx)
Screening		Class1	n ( xx.x%)	n ( xx.x%)	n ( xx.x%)	n ( xx.x%)
		Class2	n ( xx.x%)	n ( xx.x%)	n ( xx.x%)	n ( xx.x%)
Dosing	Prior start of hypoglycemic procedure	Class1	n ( xx.x%)	n ( xx.x%)	n ( xx.x%)	n ( xx.x%)
		Class2	n ( xx.x%)	n ( xx.x%)	n ( xx.x%)	n ( xx.x%)
Dosing	30min post dose	Class1	n ( xx.x%)	n ( xx.x%)	n ( xx.x%)	n ( xx.x%)
		Class2	n ( xx.x%)	n ( xx.x%)	n ( xx.x%)	n ( xx.x%)
...						
Follow up		Class1	n ( xx.x%)	n ( xx.x%)	n ( xx.x%)	n ( xx.x%)
		Class2	n ( xx.x%)	n ( xx.x%)	n ( xx.x%)	n ( xx.x%)

PROGRAM SOURCE:###, DATA CUT OFF DATE: ddmmmyyy

RUN DATE: ddmmyy hh:mm CET

*Programmer Note: This table is repeated (as byvars) for each of the following Vital signs parameter: Systolic blood pressure [mmHg], Pulse rate [bpm] and body temperature [°C]*

Zealand Pharma A/S  
Protocol Number: ZP4207-17086

Clinical Study Report Section 14  
Page 1 of 1

14.3.5.6: Immunogenicity - occurrence of ADA, Safety analysis set

	dasiglucagon (N=xxx)	Placebo (N=xxx)	GlucaGen (N=xxx)	Total (N=xxx)
Occurrence of ADA				
No	n ( xx.x%)	n ( xx.x%)	n ( xx.x%)	n ( xx.x%)
Yes	n ( xx.x%)	n ( xx.x%)	n ( xx.x%)	n ( xx.x%)
Missing	n	n	n	n

PROGRAM SOURCE:###, DATA CUT OFF DATE: ddmmmyyy

RUN DATE: ddmmyy hh:mm CET

14.4.1.1: Summary statistics of plasma dasiglucagon and GlucaGen concentration table, FAS

Treatment	Variable	Pre-dose	10min	20min	30min	40min	60min	90min	140min	220min	300min	
Glucagon	Result	n	xx	xx	xx	xx	xx	xx	xx	xx	xx	
		Mean (SD)	xx.x (xx.xx)	xx.x (xx.xx)	xx.x (xx.xx)	xx.x (xx.xx)	xx.x (xx.xx)	xx.x (xx.xx)	xx.x (xx.xx)	xx.x (xx.xx)	xx.x (xx.xx)	xx.x (xx.xx)
		Median	xx.x	xx.x	xx.x	xx.x	xx.x	xx.x	xx.x	xx.x	xx.x	xx.x
	Min, Max	xx, xx	xx, xx	xx, xx	xx, xx	xx, xx	xx, xx	xx, xx	xx, xx	xx, xx	xx, xx	
	Change from baselinen	n	xx	xx	xx	xx	xx	xx	xx	xx	xx	xx
		Mean (SD)	xx.x (xx.xx)	xx.x (xx.xx)	xx.x (xx.xx)	xx.x (xx.xx)	xx.x (xx.xx)	xx.x (xx.xx)	xx.x (xx.xx)	xx.x (xx.xx)	xx.x (xx.xx)	xx.x (xx.xx)
		Median	xx.x	xx.x	xx.x	xx.x	xx.x	xx.x	xx.x	xx.x	xx.x	xx.x
		Min, Max	xx, xx	xx, xx	xx, xx	xx, xx	xx, xx	xx, xx	xx, xx	xx, xx	xx, xx	xx, xx
	dasiglucagon	Result	n	xx	xx	xx	xx	xx	xx	xx	xx	xx
			Mean (SD)	xx.x (xx.xx)	xx.x (xx.xx)	xx.x (xx.xx)	xx.x (xx.xx)	xx.x (xx.xx)	xx.x (xx.xx)	xx.x (xx.xx)	xx.x (xx.xx)	xx.x (xx.xx)
Median			xx.x	xx.x	xx.x	xx.x	xx.x	xx.x	xx.x	xx.x	xx.x	xx.x
Min, Max		xx, xx	xx, xx	xx, xx	xx, xx	xx, xx	xx, xx	xx, xx	xx, xx	xx, xx	xx, xx	

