Change from baselinen		n	xx	xx	xx	xx	xx	xx	xx	xx	xx	xx
		Mean (SD)	xx.x (xx.xx)	xx.x (xx.xx)	xx.x (xx.xx)	xx.x (xx.xx)	xx.x (xx.xx)	xx.x (xx.xx)	xx.x (xx.xx)	xx.x (xx.xx)	xx.x (xx.xx)	xx.x (xx.xx)
		Median	xx.x	xx.x	xx.x	xx.x	xx.x	xx.x	xx.x	xx.x	xx.x	xx.x
		Min, Max	xx, xx	xx, xx	xx, xx	xx, xx	xx, xx	xx, xx	xx, xx	xx, xx	xx, xx	xx, xx

Pre-dose results LLOQ are set to 0 pmol/mL  
Results are rounded to 3 significant digits

PROGRAM SOURCE:###, DATA CUT OFF DATE: ddmmmyyyy

RUN DATE: ddmmmyyy hh:mm CET

*Programmer Note: The mean (SD) column above is broken into 2 lines above, but if possible put it in one row*

14.4.1.2: PK metrics, FAS

PK Parameter		dasiglucagon (N=xxx)	GlucaGen (N=xxx)	Total (N=xxx)
Cmax [pmol/L]	n	xx	xx	xx
	Mean (SD)	xx.x (xx.xx)	xx.x (xx.xx)	xx.x (xx.xx)
	Median	xx.x	xx.x	xx.x
	Min, Max	xx, xx	xx, xx	xx, xx
	Geom. Mean	xx, xx	xx, xx	xx, xx
	Gem. Mean CV %	xx, xx	xx, xx	xx, xx
Tmax [h]	n	xx	xx	xx
	Mean (SD)	xx.x (xx.xx)	xx.x (xx.xx)	xx.x (xx.xx)
	Median	xx.x	xx.x	xx.x
Min, Max	xx, xx	xx, xx	xx, xx	
...				

Results are rounded to 3 significant digits

[figure not shown]
PROGRAM SOURCE:###, DATA CUT OFF DATE: ddmmyyyy

RUN DATE: ddmmyy hh:mm CET

14.4.1.3: Figure: Mean analyte concentrations versus time - original scale, FAS

PROGRAM SOURCE:###, DATA CUT OFF DATE: ddmmyyyy

RUN DATE: ddmmyy hh:mm CET

*NOTE: This is a generic example using example data not real data*

14.4.1.4: Figure: Mean analyte concentrations versus time - log scale, FAS

[figure not shown]
→ Repetition of figure 14.4.1.3 using logarithmic y-scale

Zealand Pharma A/S  
Protocol Number: ZP4207-17086

Clinical Study Report Section 14  
Page 1 of x

14.4.1.5: Figure: Individual analyte concentrations versus time curves- original scale, FAS

PROGRAM SOURCE:###, DATA CUT OFF DATE: ddmmmyyy

RUN DATE: ddmmmyyy hh:mm CET

*NOTE: This is a generic example using example data not real data and coloring will be the same as in the figure before; x-axis and sampling scheme will be adapted to the study specifics*

14.4.2.1: PD metrics, FAS

PK Parameter		dasiglucagon (N=xxx)	Placebo (N=xxx)	GlucaGen (N=xxx)	Total (N=xxx)
Cmax [pmol/L]	n	xx	xx	xx	xx
	Mean (SD)	xx.x (xx.xx)	xx.x (xx.xx)	xx.x (xx.xx)	xx.x (xx.xx)
	Median	xx.x	xx.x	xx.x	xx.x
	Min, Max	xx, xx	xx, xx	xx, xx	xx, xx
Tmax [h]	n	xx	xx	xx	xx
	Mean (SD)	xx.x (xx.xx)	xx.x (xx.xx)	xx.x (xx.xx)	xx.x (xx.xx)
	Median	xx.x	xx.x	xx.x	xx.x
	Min, Max	xx, xx	xx, xx	xx, xx	xx, xx
...					

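### The PK outputs group children by randomized arm although exposure follows the product injected; relabel them to the as-received set

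*SAP*

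**What the plan says.** SAP section 8 defines three analysis sets and no PK set. The FAS consists of "All patients of the safety analysis set", so both sets hold the same children, but they are grouped differently. For the FAS, "Treatment assignment will be based on the randomized treatment"; for the safety set, "Treatment assignment will be based on the treatment actually received".

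SAP section 12 describes the PK analysis by treatment group and names no analysis set. The choice appears only in Appendices C and D, where both PK tables and all three PK figures carry the FAS label, for example "14.4.1.1: Summary statistics of plasma dasiglucagon and GlucaGen concentration table, FAS", "14.4.1.2: PK metrics, FAS" and "14.4.1.3: Figure: Mean analyte concentrations versus time - original scale, FAS".

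Protocol 7.4.10 keeps specialty-laboratory staff unblinded "to make sure that dasiglucagon or GlucaGen® administration is matched with the applicable bioanalytical assay". SAP section 12.2 adds that samples from children receiving placebo will not be assayed for either analyte. Protocol 12.2 includes "Incorrect treatment allocation" in its default list of major deviations.

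**The concern.** Grouping by randomized arm protects a randomized efficacy comparison. PK here is descriptive, and the stated objective is the PK profile of dasiglucagon, which is a property of the drug that entered the child. When the product given differs from the product assigned, the analyte measured and the group label come apart. The FAS keeps that child under the assigned label. The SAP already has an as-received grouping for safety and does not use it for PK.

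At stake is the descriptive accuracy of two small PK groups in children. No hypothesis test is involved.

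**Working it through.** **1. What the labels do to a misallocated child** (assay matched to the product given)

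| Randomized to | Given | Result in the PK outputs as labelled |
|---|---|---|
| dasiglucagon | GlucaGen | glucagon profile in the dasiglucagon group |
| GlucaGen | dasiglucagon | dasiglucagon profile in the GlucaGen group |
| either active product | placebo | no assay; 19 or 9 profiles remain |
| placebo | either active product | belongs to neither by-arm group; the PK shells have no placebo group |

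Under as-received grouping, the first row turns groups of 20 and 10 with one wrong profile into groups of 19 and 11 with none wrong.

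**2. Group sizes.** SAP section 5 plans 20 dasiglucagon, 10 placebo and 10 GlucaGen children, with 90% power for dasiglucagon against placebo. That figure reproduces. Exponential medians of 10 and 50 minutes give hazards ln2/10 = 0.0693 and ln2/50 = 0.0139. The 45-minute event probabilities are 1 − 2^(−4.5) = 0.956 and 1 − 2^(−0.9) = 0.464. The standard error of the hazard difference is √(0.0693²/(0.956×20) + 0.0139²/(0.464×10)) = 0.0171. Then z = 0.0555/0.0171 − 1.96 = 1.28, which is power 0.90. The figure is not in dispute and PK labelling does not affect it.

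**3. Head count.** 1/20 = 5% and 1/10 = 10%. These are shares of children, not shifts in a PK parameter.

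**4. Cmax.** If one of n profiles has expected wrong-to-right ratio r, the geometric mean moves by r^(1/n) − 1. Protocol 5.1 gives a 90% confidence interval of 0.8850 to 1.1991 for adult Cmax at 0.6 mg dasiglucagon against 1.0 mg GlucaGen.
- n = 20: 0.8850^(1/20) − 1 = −0.6%; 1.1991^(1/20) − 1 = +0.9%.
- n = 10: 0.8850^(1/10) − 1 = −1.2%; 1.1991^(1/10) − 1 = +1.8%.

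Inverting the ratio reverses the signs and leaves the sizes unchanged to this precision.

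**5. tmax.** With the adult medians in Protocol 5.1 (35 minutes for dasiglucagon, 20 for GlucaGen) as stand-ins, the mean moves by (20 − 35)/20 = −0.75 minutes in the dasiglucagon group or (35 − 20)/10 = +1.5 minutes in the GlucaGen group.

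**6. AUC.** Protocol 5.1 says only that total exposure was higher with dasiglucagon and gives no ratio. The ratios below are therefore assumptions.

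| Assumed r | Shift, n = 20 | Shift, n = 10 |
|---|---|---|
| 0.5 | −3.4% | −6.7% |
| 2 | +3.5% | +7.2% |
| 4 | +7.2% | +14.9% |

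**7. Dose in CL/f and Vz/f.** SAP section 12 divides a dose by AUC without saying planned or given. If the planned 0.6 mg were used for a child given 1 mg GlucaGen, that child's CL/f would be multiplied by 0.6/1.0 = 0.6. In the reverse case the factor is 1.0/0.6 = 1.67.

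**8. How often.** The documents give no error rate. For assumed per-child rates of 0.5%, 1% and 5%, the chance of at least one misallocation among 40 children is 1 − (1 − p)^40 = 18%, 33% and 87%. The spread shows only that the answer depends on an unknown rate.

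**The case against.** The strongest reply is that the two labels give identical tables unless an error occurs, and the protocol has controls against one: IWRS-assigned dispensing unit numbers, uniquely numbered kits, preparation to the IWRS prescription, and accountability checks by an unblinded monitor. Dasiglucagon comes in a pre-filled syringe and GlucaGen as a kit to reconstitute, so confusing those two is harder than confusing dasiglucagon with placebo. All of this stands. A reader might infer that a mix-up is likely; the documents do not support that. They also do not say that doses are prepared at the bedside, only that foil-wrapped syringes protect the blind there.

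A second reply is that the treatment-masked review in Protocol 12.2 can exclude patients or data, and that medication errors must be reported on SAE timelines. A known error would therefore probably be examined. But the consequence named for a major deviation is possible exclusion from the PPS, which no PK output uses, and FAS exclusion is foreseen only for several major eligibility violations or a complete absence of efficacy data. The review may remove the profile but need not. Removal would also discard a valid profile that belongs in the other group.

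A third reply is that the protocol does not say whether the laboratories work from the randomization list or the administration record. If they use the list, a misallocated child's samples would go to the assay for the product not given, and relabelling alone would not repair that. This stands as a limit. Listing every mismatch would at least make such a child visible.

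Finally, as-received PK beside as-randomized glucose data would put a misallocated child in different groups for exposure and response. That is a real but small cost.

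**Conclusion.** The point holds as a minor specification gap. The stated labels misclassify exposure whenever a child receives the wrong product, and a suitable set already exists. On the adult Cmax interval, one such child shifts the geometric mean by less than about 1% (n = 20) or 2% (n = 10). That interval describes adult averages at 1.0 mg GlucaGen. An individual child could differ more, and it does not cover children below 25 kg, who are assigned 0.5 mg GlucaGen. The AUC effect remains unknown.

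Two stronger readings are not supported. One is that the PK results would be wrong by 5% or 10%; those figures are head counts. The other is that the FAS definition is faulty or that efficacy is at risk. Grouping the FAS by randomized treatment is correct for efficacy, and the primary test, its power and the testing hierarchy do not depend on the PK labels.

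**What to change.** - In SAP Appendices C and D, change the set for outputs 14.4.1.1 to 14.4.1.5 from FAS to the safety analysis set (treatment actually received), limited to children given dasiglucagon or GlucaGen. Add one sentence to section 12 saying so.
- State in section 12 that CL/f and Vz/f use the dose actually given.
- List every child whose received product differs from the randomized one, and footnote that such a child appears in different groups for PK and glucose outputs.
- Leave the FAS definition and all efficacy and PD outputs as randomized.

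The cost is five labels, two sentences, a short listing and a footnote. No new data are needed. The randomization, drug administration and concentration listings are already planned (16.2.5.2, 16.2.5.5 and 16.2.5.7), and Appendix C allows minor changes to the output index without amending the SAP. The change should be made before the blind is broken, because SAP section 6 treats later analyses as post hoc.

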### **Per protocol set (PPS)**

All patients of the FAS for whom no relevant protocol deviations were documented. Treatment assignment will be based on the randomized treatment. Assignment to the stratification factor injection site will be based on the planned and not the actual used injection site.

The analysis of the primary endpoint will be based on the FAS. A secondary analysis of the primary endpoint will be based on the PPS. Safety analysis will be based on the safety analysis set.

The decision whether a protocol deviation is relevant or not for the exclusion of patients from the PPS will be made case-by-case in a data review meeting before breaking the blind.

## **9. STUDY POPULATION**

### **9.1 Patient Disposition**

Patient disposition information will be summarized for all patients by treatment group. Summaries will include: the number of patients screened, the number of randomized patients, and the number of patients in each analysis set.

The number of patients who completed or discontinued the study will be tabulated by treatment. In addition, for patients who discontinued, the primary reason will be tabulated by treatment group.

Patient numbers and percentages in each country and patient numbers and percentages in each country and center will be presented by treatment group. In addition, the number of patient numbers and percentages of US versus non-US countries will be tabulated by treatment group.

### **9.2 Protocol Deviations**

A listing of all protocol deviations including the deviation designation (relevant/non-relevant), category, and indication of whether the deviation led to an exclusion of a patient from the PPS will be presented in a data listing.

### **9.3 Eligibility**

A listing of patients not fulfilling any eligibility criteria will be created. This listing will consider and differentiate eligibility criteria at screening as well as the re-check of dosing day exclusion criteria.

## 9.4 Demographic and Baseline Characteristics

Demographic variables include: age, age group (6-11 years, 12-17 years), sex, childbearing potential, ethnicity, and race.

Summary statistics will be presented for the above-mentioned variables by treatment group.

Other baseline characteristics include: diabetes history, medical history and body measurements (height, weight, BMI).

BMI will be additionally classified into the following categories:

<25

25-<30

30-<35

>=35

A summary table for BMI by BMI class and country will be created. In addition, this table will show BMI classes of US versus non-US countries.

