7.2 Discussion of trial design and choice of control groups

The trial will be randomized and double-blind to increase trial validity and to reduce bias during evaluation of assessments with the treatments. Since the 3 trial products are not identical in appearance, (dasiglucagon and placebo are liquid formulations and GlucaGen® is available as a powder for reconstitution), unblinded trial personnel, who will not be involved in other trial procedures and assessments, will do the handling, preparation and administration of trial product. Blinded trial personnel will do all trial assessments performed at the trial center.

Children with T1DM will be randomized 2:1:1 in order to evaluate the efficacy and safety of dasiglucagon compared to placebo and GlucaGen® and PK/PD parameters. The randomized, double-blind, parallel arm design with administration of a single dose of randomized trial product (dasiglucagon, placebo or GlucaGen®) will allow a relative comparison between the 3 treatment arms.

Dasiglucagon will be administered at fixed doses independent of body weight because this is the intended therapeutic dosing regimen in the emergency treatment of hypoglycemia. The selected dose of 1 mg GlucaGen® is the recommended dose for treatment of severe hypoglycemia (in accordance with the label, children below 25 kg body weight will be administered 0.5 mg GlucaGen®). Based on pre-clinical and clinical studies in adult patients, it has been demonstrated that 0.6 mg of dasiglucagon results in an initial PD response (i.e. acute glucose mobilization) comparable to 1 mg GlucaGen® (see also [Section 5.1](#)).

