7.3.1 Inclusion criteria

To be included in the trial, patients have to fulfill all of the following criteria:

1. Following receipt of verbal and written information about the trial, patient, parent(s) or guardian(s) of the patient must provide signed informed consent before any trial-related activity is carried out*
2. Female or male patients with T1DM for at least 1 year, diagnostic criteria as defined by the American Diabetes Association, and receiving daily insulin and in good and stable medical condition
3. At least 6.0 years of age (inclusive) and less than 18.0 years
Germany only: A “staggered approach” will be applied, whereby a positive safety assessment needs to be available for at least 10 patients who have completed the dosing visit in the overall trial before younger patients (6 to 11 years of age) may be enrolled.
4. Body weight ≥ 20 kg
5. Female patients must meet one of the following criteria:
 - a. Participant is of childbearing potential and agrees to use one of the accepted contraceptive regimens throughout the entire duration of the trial from screening until last follow-up visit. An acceptable method of contraception includes at least one of the following:
 - i. Abstinence from heterosexual intercourse
 - ii. Systemic contraceptives (birth control pills, injectable/implant/ insertable hormonal birth control products, transdermal patch); if the participant is using

- systemic contraceptives, she must use an additional form of acceptable contraception (iii or iv, below)
- iii. Intrauterine device (with and without hormones)
 - iv. Condom with spermicide
- or
- b. Participant is of non-childbearing potential due to pre-puberty status or a medical condition confirmed by the investigator
6. Male patients must meet the following criteria: If sexually active, uses condom and partner practices contraception during the trial from screening and until last follow-up visit
7. Willingness to adhere to the protocol requirements
- * Informed consent signatures must be obtained according to local regulations.

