7.4.6 Selection of doses in the trial

The selected dose of 1 mg GlucaGen[®] is the recommended dose for treatment of severe hypoglycemia (in accordance with the label, children below 25 kg body weight will be administered 0.5 mg GlucaGen[®]). Pre-clinical and adult clinical studies demonstrated that 0.6 mg of dasiglucagon results in an initial PD response (i.e. acute glucose mobilization) comparable to 1 mg GlucaGen[®].

The estimation of the dasiglucagon dose in the pediatric trial is based on a PK and PD approach⁶ where a previously developed population PK/PD model³ for dasiglucagon was extended with an allometric scaling component for the PK model⁴. The PD response was assumed to be similar in pediatric and adult patients as organ maturation for patients above 4 years is assumed not to have a meaningful impact on dasiglucagon PD. The pediatric PK component was developed by allometric scaling of clearance (Cl) and volume (V) by body weight from published glucagon PK data obtained from 2 clinical trials following intramuscular administration to pediatric (4 to 17 years) and adult T1DM patients^{11,9}.

The conclusion of the modelling was that a dose of 0.6 mg appears appropriate to ensure a fast rescue from hypoglycemia for adult patients and children down to a weight of 25 kg. Although the dasiglucagon C_{max} and AUC is expected to be higher in children, it does not exceed the total C_{max} and AUC obtained in adults previously administered 2 mg dasiglucagon. The higher total drug exposure (AUC and C_{max}) at lower weight is partially compensated by the shorter t_{1/2} and saturated PD response. The resulting total time of drug exposure and PD effect (AEU and CE_{max}) is similar throughout the weight range.

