The primary endpoint will additionally be analyzed using a discrete-time Cox proportional hazards (CPH) time to event statistical model, if the hazards by treatment group can be assumed

proportional using a graphical comparison of log-minus-log survival curves and no more than two-thirds of the recovery times are censored in each treatment group. The CPH model will be used for descriptive purposes, with treatment group, age group and injection site modeled as categorical effects, and baseline plasma glucose modelled as a continuous covariate. The treatment group hazard ratios of active versus placebo, will be estimated together with the 95% confidence intervals, and pairwise treatment group inferences (dasiglucagon vs placebo, GlucaGen vs placebo, dasiglucagon vs GlucaGen) will be evaluated using least-square mean and standard deviation estimates.

Due to the discrete nature of blood sampling in time, and the fact that there must be a true, but unmeasured, ordering of the recovery times, the method using the “exact discrete” partial likelihood for tied failure times will be applied. In SAS, this is implemented in the `phreg` procedure with the option `ties=discrete`. The influence of age and injection site on time to recovery will also be evaluated in the proportional hazards model by a ‘type 3’ test in the `phreg` procedure.

In addition, separate CPH models will be calculated to evaluate homogeneity for the following factors:

Sex, BMI class, ethnicity, race, US/non-US.

These additional homogeneity models are only presented for the primary efficacy analysis, but not for subsequent variants of that analysis.

To obtain an estimate of these true, but unassessed, patient recovery times, a linear interpolation (between the two time points before and after recovery is observed) will be carried out to estimate the patients’ actual time of recovery. These derived recovery times will be described and analysed in the same manner as for the discrete times above.

Let  $t_1$  and  $t_2$  be the 2 time points before and after recovery is observed and  $y_1$  and  $y_2$  be the corresponding changes from baseline in glucose concentrations, where  $y_1$  is below 20 mg/dL and  $y_2$  is greater than 20 mg/dL.

The interpolated time point  $t_{ext}$  is calculated then as:

$$t_{ext} = t_1 + \frac{(20 - y_1) * (t_2 - t_1)}{(y_2 - y_1)}$$

This linear interpolation is only used as a supportive analysis to the primary analysis model using `proc lifetest`.

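### The homogeneity check by BMI class (cut-offs 25/30/35) is likely to be uninformative about body size in children aged 6 to under 18

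*SAP*

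**What the plan says.** SAP 9.4 lists BMI among the baseline characteristics and adds that "BMI will be additionally classified into the following categories", namely <25, 25 to <30, 30 to <35 and >=35. The classes feed a summary by country and US versus non-US.

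They also enter the efficacy analysis. SAP 11.1 says "In addition, separate CPH models will be calculated to evaluate homogeneity for the following factors", and the factors are "Sex, BMI class, ethnicity, race, US/non-US". The shell for Table 14.2.1.1 prints a hazard ratio versus placebo with a 95% interval for each subgroup level. The Cox model is run only if hazards look proportional and "no more than two-thirds of the recovery times are censored in each treatment group".

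Protocol 7.3.1 admits children who are "At least 6.0 years of age (inclusive) and less than 18.0 years", with "Body weight ≥ 20 kg". Protocol 7.2 states that "Dasiglucagon will be administered at fixed doses independent of body weight". Protocol 7.4.6 expects higher AUC and Cmax in children, an excess that "at lower weight is partially compensated by the shorter" half-life and by a saturated glucose response.

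Weight and height are otherwise summarised by arm and listed. No efficacy model contains weight, continuous BMI or a treatment-by-size term. Age group enters the Cox model as a main effect only.

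**The concern.** One set of fixed cut-offs is applied from age 6 to 17. A light young child and a lean adolescent both fall below 25, so the lowest class mixes the children with the highest expected exposure with much heavier ones. The other three classes share whoever is left, across three arms.

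A hazard ratio versus placebo needs placebo recoveries in the class concerned. Without any, the estimate is infinite or not estimable. The table would then show blank or extreme entries under a homogeneity label, and a reader could mistake the absence of a visible difference for evidence that body size does not matter.

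**Working it through.** **The plan's own figure.** SAP 5 and Protocol 10.2 give 90% power with 20 versus 10 patients, exponential medians of 10 and 50 minutes, 45 minutes of follow-up and two-sided 5%.
- Recovery by 45 minutes: dasiglucagon 1 − 2^(−45/10) = 0.956; placebo 1 − 2^(−45/50) = 0.464. Expected recoveries are 20 × 0.956 = 19.1 and 10 × 0.464 = 4.6.
- Hazards: ln2/10 = 0.0693 and ln2/50 = 0.0139, difference 0.0555.
- Unpooled SE: √(0.0693²/19.1 + 0.0139²/4.6) = 0.0171.
- Power: Φ(0.0555/0.0171 − 1.96) = Φ(1.28) = 90.0%. The figure is reproduced and does not depend on the BMI classes.

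**Height at which BMI equals 25.** Height = √(weight/25). Protocol 5.2 gives pediatric weight groups of 25.4 (SD 5.2), 43.2 (SD 8.9) and 61.2 (SD 13.8) kg. At the means, BMI reaches 25 only at or below 1.01, 1.31 and 1.56 m; at the 20 kg entry limit, 0.89 m. One SD above the heaviest mean, at 75 kg, the height is 1.73 m, so some adolescents will exceed 25.

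**Share below 25 (assumption).** The documents give no heights. I assumed one height per weight group, normally distributed weights and equal group sizes. Share = Φ((25 × height² − mean)/SD). For example, at 1.67 m in the heaviest group: Φ((69.7 − 61.2)/13.8) = 73%.

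| Assumed heights (cm) | Lightest | Middle | Heaviest | Overall |
|---|---|---|---|---|
| 120 / 140 / 158 | 97.9% | 74.3% | 53.5% | 75% |
| 125 / 148 / 167 | 99.6% | 90.3% | 73.2% | 88% |
| 130 / 154 / 175 | 99.9% | 96.5% | 86.7% | 94% |

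Of 40 patients, 30 to 38 would be below 25, leaving 2 to 10 for three classes and three arms.

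**Placebo information at BMI 25 or more.** Let s be the share reaching 25. The expected number of placebo patients is 10s, the chance of none is (1 − s)^10, and the chance of no placebo recovery is (1 − 0.464s)^10.

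| s | Placebo patients | Average per upper class | No placebo patient | No placebo recovery |
|---|---|---|---|---|
| 25% | 2.5 | 0.8 | 6% | 29% |
| 10% | 1.0 | 0.3 | 35% | 62% |
| 5% | 0.5 | 0.2 | 60% | 79% |

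The last column pools all three upper classes; each single class is worse.

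**What a better split could achieve.** Take Var(log HR) = 1/d₁ + 1/d₀, with d the recoveries per arm. In a balanced half, d₁ = 9.6 and d₀ = 2.3, so the 95% interval is the estimate times or divided by about 4.2. In the small class of a 90/10 split, d₁ = 1.9 and d₀ = 0.46, and the factor is about 25. Power for a ratio of hazard ratios of 2, 3 or 5 is 10%, 18% or 34% with the balanced split, against 6%, 9% or 15% with 90/10.

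**Whether the model runs.** More than two-thirds of 10 placebo patients censored means at least 7. With censoring probability 1 − 0.464 = 0.536, the binomial chance is 24%.

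**The case against.** The strongest reply is that little hangs on this. SAP 11.1 calls the Cox model descriptive, SAP 10.7 leaves these models out of the testing hierarchy, and the model may not run at all. Weight, height and BMI are collected and listed, so no data are lost. All of that stands, and it limits the importance of the point.

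A second reply is that the documents predict no problem. Protocol 5.2 expects similar total and maximum glucose response from 25 to 77 kg, and Protocol 7.4.6 expects a similar effect throughout the weight range; it is exposure that varies. A reader might infer that body size is the main effect modifier here. The documents do not support that. The prediction is nevertheless model-based and its stated range begins at 25 kg, whereas enrolment begins at 20 kg, so a check that can produce an estimate has some value.

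A third reply is that 10 placebo patients, rather than the cut-offs, are the main limit. This also stands: no choice of size measure gives good power. The cut-offs make a weak check weaker and often inestimable.

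**Conclusion.** The point holds as a minor one. The BMI-class model is likely to be uninformative: a 29% to 79% chance of no finite hazard ratio versus placebo at BMI 25 or more, for assumed shares of 25% down to 5% and the plan's own placebo recovery assumption.

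Two stronger readings are tempting and are not supported:
- That nearly every child falls in one class. No BMI distribution is documented, and the assumed heights give a range starting at three quarters. Most children, and almost all of the lightest, is as far as it goes.
- That the upper placebo cells will be empty. The chance of no placebo child at 25 or more is 6% to 60% over the same shares, so this is a risk and not a certainty.

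The primary comparison, its stated power and the testing hierarchy are untouched.

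**What to change.** In SAP 11.1, replace BMI class in the homogeneity models with body weight as a continuous covariate plus a treatment-by-weight interaction. Age- and sex-standardised BMI is an alternative; raw BMI is less suitable because it mixes body size with age. Keep age group in the model. Report the interaction estimate with its 95% CI and label it descriptive. Base the reading on dasiglucagon versus placebo, because the GlucaGen dose itself changes at 25 kg.

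The BMI-by-country table in SAP 9.4 can stay; nothing here shows a fault in it. Two wording points can be settled in the same edit: the top class is >=35 in SAP 9.4 but >35 in the table shells, and SAP 10.6 plans no subgroup analysis while the shell for Table 14.2.1.1 prints subgroup-level hazard ratios.

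The cost is SAP text, one table shell and programming, using data already collected. The drawback is that the estimate stays imprecise, and weight is correlated with age, so the two cannot be cleanly separated in 40 children.
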